6.3 Unscheduled Visits

In the event of a suspected AE that needs evaluation by the PI or needs laboratory testing or intervention, a subject may schedule a visit at any time. During their baseline visit, instructions will be provided detailing how to schedule a visit. These instructions will include a phone number and office address that subjects may use to contact the study group. During unscheduled visits, study treatment will not be administered and assessments will not be performed.

6.4 Sample Collection, Preparation, Labeling and Shipment

6.4.1 Sample collection

All samples will be collected as specified in the schedule of events flowchart and as per SOP of the respective institution.

6.4.2 Labeling and de-identifying specimens

Specimens will not have patient identifiers attached to them (i.e., name, initials, DOB, or social security number). They will be labeled with a unique patient ID number or code and date of visit. The key to the code will be kept at each institution in a password-protected computer, to be accessed only by the clinical staff at each institution delegated to this task. Should a specimen be transported to Mount Sinai Medical Center with any patient identifiers, the specimen will be returned to Northwestern for proper labeling.

6.4.3 Transporting specimens to Mount Sinai Medical Center

All specimens will be transported to Mt. Sinai either by hand by a member of the investigative staff (if acquired at Mt. Sinai) or by competent courier (eg. Fedex) for the frozen skin and blood samples. Biobanked serum and PAX RNA samples, swabs for microbiome and a buccal swab for future pharmacogenomics will be retained in the [name] lab. The shipment will be traceable and that the chain of custody will be documented. The specimens will be delivered to a competent member of the study team, who will assure that the specimens have been properly de-identified and stored/transported in the proper environment (see above).

6.4.4 Specimen management

Specimens will be logged into a password protected electronic database by a qualified member of the research team. Samples will be stored at the storage facility for a period of at least 5 years following the date the analysis is complete and used solely for objectives outlined in this study. After this date, residual sera will be destroyed. Patient confidentiality will be maintained. Results of all experiments will be reviewed by one of the PIs and the source of the data will be verified. Regular meetings of the specimen/data analysis team will occur. Regular study monitoring will also occur by qualified members of the research

Product: Secukinumab

Protocol Number: CAIN457AUS05T

Date: 14 July 2018

30

team. The samples will be retained for 5 years from the end of the clinical completion of the study. In addition, samples can be destroyed at any time at the request of the subject.

7. SAFETY DATA COLLECTION, RECORDING AND REPORTING

7.1 Adverse Events

An adverse event (AE) is any untoward medical occurrence experienced by a subject after completing written informed consent to participate in a clinical study. AEs may not be causally or temporally associated with the investigational product or procedure. Lack of drug effect is not considered an AE because the purpose of the study is to establish drug effect.

All AEs and SAEs will be recorded and reported from the time the subject signs the informed consent form to 4 weeks after administration of the last dose of test article. Subjects will be instructed to report AEs and SAEs during this time period. The investigators will follow up on all AEs and SAEs until the events have subsided, returned to baseline, or in case of permanent impairment, until the condition stabilizes.

Aggregated AEs will be evaluated monthly by the PI/research teams. Safety data will be reviewed by the investigators, study teams, biostatisticians and a monitor unrelated to the study approximately every 3 months, depending on the number of subjects enrolled. A DSMB will be organized to assess safety and overall risk to benefit ratio throughout the study. The DSMB will meet via phone conference quarterly or as deemed necessary by the PIs. The first DSMB meeting via a phone conference will be assembled after the first 3 months (or 8 patients, whichever is first) are enrolled to assure that the study is proceeding according to expectations and no changes in the protocol and consent are needed. An independent safety monitor in each institution will assure that the data is correctly gathered, recorded, and assembled concisely and accurately for DSMB review.

Most notable side effects per secukinumab Full Prescribing Information include increased risk of infection (including but not limited to nasopharyngitis, upper respiratory tract infection, and mucocutaneous infections with candida), exacerbations and new cases of inflammatory bowel disease, and hypersensitivity reactions. Adverse reactions reported by greater than 1% of subjects also include diarrhea, rhinitis, oral herpes, pharyngitis, urticaria, and rhinorrhea. Adverse reactions reported by less than 1% of subjects include sinusitis, tinea pedis, conjunctivitis, tonsillitis, oral candidiasis, impetigo, otitis media, otitis externa, increased liver transaminases, and neutropenia. There is an increased prevalence of staphylococcal and fungal cutaneous infections in ichthyosis, and patients respond normally to traditional anti-bacterial and anti-fungal agents when detected. Investigators will be vigilant to the possibility that patients with ichthyosis will experience an increased incidence of these infections; if discovered, mucocutaneous infection will be treated with standard measures.

7.2 Unblinding and Followup of Subjects with Adverse Events

If a subject develops an adverse event that requires early termination, then we will document whether they were receiving secukinumab or placebo.

Product: Secukinumab

Protocol Number: CAIN457AUS05T

Date: 14 July 2018

31

If subjects are experiencing unresolved adverse events at the time of study completion or early termination, then the investigator will schedule a follow-up visit to determine the outcome of the adverse event.

7.3 Serious adverse events

7.3.1. Definition of SAE

A serious adverse event (SAE) is any adverse event which:

- is fatal or life-threatening
- results in persistent or significant disability/incapacity
- constitutes a congenital anomaly/birth defect
- requires inpatient hospitalization or prolongation of existing hospitalization, unless hospitalization is for:
 - routine treatment or monitoring of the studied indication, not associated with any deterioration in condition
 - elective or pre-planned treatment for a pre-existing condition that is unrelated to indication under study and has not worsened since signing the informed consent
 - treatment on an emergency outpatient basis for an event not fulfilling any of the definitions of a SAE given above and not resulting in hospital admission
 - social reasons and respite care in the absence of any deterioration in the subject's general condition
- is medically significant, i.e., defined as an event that jeopardizes the subject or may require medical or surgical intervention

All malignant neoplasms will be assessed as serious under “medically significant” if other seriousness criteria are not met.

Life-threatening in the context of a SAE refers to a reaction in which the subject was at risk of death at the time of the reaction; it does not refer to a reaction that hypothetically might have caused death if more severe or ongoing.

Medical and scientific judgment should be exercised in deciding whether other situations should be considered serious reactions, such as important medical events that might not be immediately life threatening or result in death or hospitalization but might jeopardize the subject or might require intervention to prevent one of the other outcomes listed above.

Examples of such events are intensive treatment in an emergency room or at home for allergic bronchospasm, blood dyscrasias or convulsions that do not result in hospitalization or development of dependency or abuse.

Any suspected transmission via a medicinal product of an infectious agent is also considered a serious adverse reaction.

All AEs (serious and non-serious) are captured on the case report form; SAEs also require individual reporting to DSMB and to Novartis Medical Affairs as per Section 7.2.2.

Product: Secukinumab

Protocol Number: CAIN457AUS05T

Date: 14 July 2018

32

7.3.2. SAE Reporting

To ensure subject safety, every SAE, regardless of causality, occurring after the subject has provided informed consent and until 30 days after the last study visit, must be reported to the DSMB within 24 hours of learning of its occurrence. SAE must also be reported to Novartis by the DSMB within 15 days per federal prompt reporting requirements. Any SAEs experienced after the 30-day period should be reported to DSMB if the investigator suspects a causal relationship to study treatment.

Recurrent episodes, complications, or progression of the initial SAE must be reported as follow-up to the original episode, regardless of when the event occurs. This report must be submitted to the DSMB within 24 hours of the investigator receiving the follow-up information. An SAE that is considered completely unrelated to a previously reported one should be reported separately as a new event.

Information about all SAEs (either initial or follow up information) is collected and recorded on the paper Serious Adverse Event Report Form. The investigator must assess the relationship of each SAE to study treatment, complete the SAE Report Form in English, and send the completed, signed form by fax within 24 hours after awareness of the SAE to the DSMB. The original copy of the SAE Report Form and the fax confirmation sheet must be kept with the subject's source documentation at the study site. Follow-up information should be provided using a new paper SAE Report Form stating that this is a follow-up to a previously reported SAE.

Follow-up information provided should describe whether the event has resolved or continues, if and how it was treated, whether the treatment code was broken or not and whether the subject continued or withdrew from study participation. Each re-occurrence, complication, or progression of the original event should be reported as a follow-up to that event regardless of when it occurs.

If the SAE is not previously documented in the Full Prescribing Information, (new occurrence) and is thought to be related to the study treatment, the DSMB may urgently require further information from the investigator. An Investigator Notification (IN) may need to be issued to inform investigators involved in any study with the same study treatment that this SAE has been reported

Deaths or any serious adverse events will be reported to the DSMB and Novartis within 24 hours of becoming aware of the event. This information will be communicated by the PI via email. The DSMB will confirm receipt by email. All serious adverse events will be reported to the IRB of each institution according to their policies, and these events will also be reported by the DSMB and Novartis. Non-serious adverse events will be reported to each Institution's IRB per their IRB's policies. SAEs will be reported to PI immediately, and if the number of subjects experiencing AEs exceeds the pre-determined threshold, a meeting will be called to evaluate and determine if an early termination is needed.

7.4. Pregnancy Reporting

To ensure subject safety, each pregnancy occurring while the subject is on study treatment must be reported the DSMB within 24 hours of learning of its occurrence, and to Novartis Medical Affairs within 15 days. The pregnancy should be followed up to determine outcome, including spontaneous or voluntary termination, details of the birth, and the presence or absence of any birth defects, congenital

Product: Secukinumab

Protocol Number: CAIN457AUS05T

Date: 14 July 2018

33

abnormalities, or maternal and/or newborn complications. This includes both cases of pregnancy with paternal or maternal exposure to investigational products.

Pregnancy should be recorded on the Clinical Trial Pregnancy Form and be reported by the investigator/qualified site staff to DSMB. Pregnancy follow-up should be recorded on the same form and should include an assessment of the possible relationship to the study treatment.

Any SAE experienced during the pregnancy must be reported on the SAE Report Form.

8. DATA REVIEW AND DATABASE MANAGEMENT

In this multicenter project, both PIs (or their designee) will be responsible for protocol development, consenting of subjects, performing skin biopsies, treatment and evaluation of subjects, review of adverse events, and reporting adverse events to the DSMB. Each site will have a project manager whose duties will include protocol development, grant administration for the individual study site, purchasing, case report form and source document design and development, and oversight of the project at the study site. An independent study safety monitor at each site will be contracted to perform review of consents, serious adverse events, and source verification on a quarterly basis throughout the study. This independent safety monitor in each institution will also assure that the data are correctly gathered, recorded, and put together concisely and accurately for prompt submission to the DCC. Thus, the audit function at each site is independent of the study research team. Data will be entered by study coordinators in a central REDCap database based at Northwestern. The Dermatology Clinical Trials Unit currently manages both international and national multisite REDCap databases. A designated data manager will manage and document all clinical data in REDCap, assuring the correct insertion and transfer of data, and aligning the institutions. The statistician will meet with the DCC every two months to discuss the progress of the study. In addition, an Executive Committee consisting of the Principal Investigators, the project managers and the study statistician will meet every other week by phone or Skype to address issues and ensure that all activities are moving forward in a coordinated manner. The DSMB will assess safety and overall risk to benefit ratio throughout the study. The DSMB will meet every 3 months to review aggregate adverse events, with additional meetings and conference calls if deemed necessary by the PIs. The first meeting via a phone conference will be assembled after the first 3 subjects are enrolled, in order to assure that the study is proceeding according to expectations and no changes in the protocol or consent are needed.

8.1. Site Monitoring

The Project Manager at Mt. Sinai will remotely monitor the Northwestern site, and the Project Manager at Northwestern will monitor the Mt. Sinai site. Sites will also be monitored internally by the Data Coordinating Center and remotely by the Data Safety Monitoring Board.

8.2. Data Collection

Demographics, medical information, and data points will be recorded. Once collected by the study staff, data for each subject will be transferred to a secure REDCap database.

8.3 Data Disclosure and Subject Confidentiality

Each subject will be given a unique identifier code. The subject's name and code will be maintained on a password protected Coded Identifier List (CIL), on a password protected computer, in a secured building.

Product: Secukinumab

Protocol Number: CAIN457AUS05T

Date: 14 July 2018

34

An additional spreadsheet with the unique identifier codes will be maintained and used for data collection. Only authorized study staff will have access to the spreadsheets.

Subject medical information obtained as a result of this study is considered confidential and disclosure to third parties other than the principal investigators and the study team is prohibited. Data generated as a result of this study will be available for inspection on request by the Institutional Review Board (IRB). Subjects' personal information collected from medical records will be maintained on the CIL. An additional spreadsheet will be maintained with only the subjects' unique codes. These spreadsheets will be maintained on password-protected computers, in password protected network folders per institutional Data Security Plan.

9. DATA ANALYSIS

Statistical analysis of all clinical and translational studies will be performed by statistician at the Icahn School of Medicine at Mount Sinai and Northwestern University. Descriptive statistics of demographics and other baseline characteristics will be presented for all subjects.

9.1. Analysis Sets

Definition of Trial Analysis Sets: All subjects who provide informed consent and are registered in the trial will be accounted for in the clinical trial report. The inclusion/exclusion of subjects and/or subject data from the trial analysis sets will be documented in the statistical analysis plan before breaking the randomization code.

'Modified Intention-to-Treat' Analysis Set: The primary analysis population will be based on a modified intention-to-treat (mITT) population, which is defined as all randomized patients who received at least one dose of the randomized treatment. Because the loading dose is given at baseline, this should effectively include all the randomized patients.

9.2. Subject Demographics and Other Baseline Characteristics

Descriptive statistics of demographics and other baseline characteristics will be presented for all subjects. Demographics include age, sex, race, ethnicity, and skin type. Other baseline characteristics include height, weight, and vital signs, concurrent diagnoses (from medical history and indications for concomitant medication), concomitant medications, and previous treatments.

9.3. Efficacy Analyses:

All data will be analyzed after the 16-week double blinded portion of the study is completed. However, all patients and blinded study personnel will remain shielded from any information regarding the data after these analyses until the conclusion of the study.

Analysis of primary efficacy endpoint

The primary efficacy endpoint is the change from baseline to week 16 in the composite IASI score. Differences in change over time in the composite IASI score between treatment and placebo will be assessed using a mixed-effect model. The model will include treatment and treatment-by visit interaction as fixed effects and study subjects as random effects. Orthogonal contrasts will be used to test differences in the treatment effect at the different time points. This model produces unbiased treatment effect, even if

Product: Secukinumab

Protocol Number: CAIN457AUS05T

Date: 14 July 2018

35

some subjects have missing values (provided that the missing data is missing at random). Besides the change in the composite IASI score, final results will be presented as percent changes from baseline, calculated from the least square means of the model above (Vickers et al, 2001).

Analysis of primary safety endpoint

Safety analyses will be presented rates of bacterial or fungal mucocutaneous infection in each treatment group from baseline through week 16. The rate of infections will be compared using poisson regression. The proportion of subjects experiencing bacterial or fungal mucocutaneous infection during the study period in each treatment group will also be reported and compared using a Fisher exact test.

Analysis of secondary efficacy endpoint

We anticipate that, given the small sample size, a formal subgroup analysis (for ARCI-LI vs ARCI-CIE vs. EI vs. NS) will not be possible. However, we will report means and 95% confidence interval to descriptively compare the performance of the treatment across the four subgroups.

To compare secukinumab to placebo according to the proportion of patients who achieve IASI50/IASI75 at week 16, a Fisher's exact test for contingency tables analysis will be used. The same approach will be used for all other binary outcomes, including a 2-point reduction in CISI, 50% (or 75%) reduction in IASI-E, EASI-S, a 3-point reduction in patient-reported itch or pain (each on a 10 point scale); and a 50% reduction in TEWL.

Mechanistic Endpoints: mRNA expression values will be normalized to housekeeping gene hARP and log₂-transformed for analysis. Measurements under the limit of detections will be imputed as 20% of the minimum value observed for that gene. Similar to the IASI score, qRT-PCR expression data was modeled using a mixed effect models.

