4.1 Inclusion Criteria

Subjects are qualified for enrollment if they meet the following criteria:

- Subject has provided informed consent
- Subjects are at least 18 years of age or older at the time of screening.
- Female subjects must not be pregnant or breast-feeding.
- Female subjects of child-bearing potential with a negative urine pregnancy test and using at least one form of contraception (abstinence allowed).
- Subjects must have a confirmed diagnosis of ARCI-CIE, ARCI-LI, EI or NS (by genotype or willingness to be genotyped).
- Subjects must be clinically judged to be immunocompetent.
- Subjects will have no allergy to secukinumab, latex, or components of the product.
- Subjects will have baseline laboratory testing (normal or non-significant CMP and CBC, and negative for HIV, hepatitis B and C, QuantiFERON®-TB gold)
- Subjects must have an erythema score of at least 18 on IASI and an IASI-E score of 12 (at least moderate severity of erythema) at baseline.

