5.4 Treatment Assignment, Randomization

At the baseline visit [day 0] eligible subjects will be randomized. A randomization number will be assigned to the subject which will be used to link the subject to a treatment arm.

Subject Identification

Subjects are numbered sequentially. Each subject will be assigned a unique number and will keep this number for the duration of the study. Subject numbers will not be reassigned or reused for any reason. Subjects should be identified only by their assigned identified code number. The investigator must maintain a subject master log linking the subject number to the subject's name. The investigator must follow all applicable privacy laws in order to protect a subject's privacy and confidentiality.

Randomization

Product: Secukinumab

Protocol Number: CAIN457AUS05T

Date: 14 July 2018

22

A centralized randomization system will be implemented at NU. After fulfilling the enrollment criteria, study participants will be randomized on day 0/baseline to secukinumab or placebo in a 1:1 ratio. Randomization will be stratified by disease subtype (ARCI-CIE, ARCI-LI, EI and NS) in random blocks of 4. We will not stratify by center due to the small sample size.

Codes will be sent from the data coordinating center (NU) and distributed to a licensed pharmacist at each study site. Records of the code/seed used to generate the randomization will be kept. The pharmacy and data management personnel will keep clinical Investigators blind through the study until all clinical data has been collected and recorded. A revision and quality control assessment of the collected data will be carried out. Once all data quality issues are sorted out, the data analysis stage will start and investigators will be unblinded. Laboratory personnel conducting assays for the mechanistic studies will be blinded.

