6.1.9 Severity Evaluations (Appendices 2-6, 9, 10)

Severity evaluations will be performed at every study visit. Severity assessments will be performed by: Ichthyosis Area and Severity Index (IASI), Congenital Ichthyosis Severity Instrument (CISI), a modified CISI (m-CISI), the Bodemer scoring system (Bodemer et al 2011), and the Yale Ichthyosis Severity

Product: Secukinumab

Protocol Number: CAIN457AUS05T

Date: 14 July 2018

27

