9.4 Safety Variables

Safety will be evaluated by tabulations of adverse events and will be presented with descriptive statistics at each visit for each treatment group. The statistical evaluations will be organized by Treatment Phase (Weeks 0-16) and Crossover/Open-label phase (16-52). The number and percentage of subjects experiencing an AE/SAE will be stratified by system organ class, or a preferred term, and severity of the adverse event, and recorded and tabulated overall by each sub-strata. Each subject will be counted only once within a system organ class or a preferred term using the adverse events with the highest severity within each category. All information pertaining to adverse events noted during the study will be listed by subject, detailing verbatim given by the investigator, preferred term, system organ class, date of onset, date of resolution, severity, and relationship to treatment. A tabulation of Serious Adverse Events (SAEs), will be provided by subject within treatment groups. The proportion of subjects in each treatment group reporting adverse events that occur in ~ 5% in either treatment group will be compared using the Fisher's exact test.

The specific system organ classes and preferred terms analyzed will be those that are reported by at least five percent of the subjects in either treatment group.

9.5. Sample size Justification:

Sample size estimation for this trial is based on the comparison of the change in the composite IASI score from baseline to 16 weeks post treatment between the secukinumab and placebo arms. Data from our cohort

Product: Secukinumab

Protocol Number: CAIN457AUS05T

Date: 14 July 2018

36

of 21 adolescents and adults was used to estimate the sample size. The mean composite IASI score in this cohort was 28.9 with a standard deviation of 9.0. Assuming a correlation between the pre and post treatment IASI scores of 0.55, we estimated the standard deviation of the baseline to week 16 change at approximately 8.5. Fixing the type I error at 0.05 for a two tailed t-test, a sample size of 16 subjects per group provides 80% power to detect a treatment effect of 30% for change in the IASI composite score (40% reduction in the secukinumab vs. an 10% reduction in the placebo arm). To account for an anticipated 20% dropout rate, 20 subjects in each treatment group (total 40) will be randomized.

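### The primary model in section 9.3 names neither baseline IASI nor the stratification factor; adjusting for both is a free gain of about 6 to 8 power points at the plan's inputs, and smaller if the entry cut-off narrows baseline

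*Combined protocol and SAP*

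**What the plan says.** Section 9.3 defines the primary efficacy endpoint as change from baseline to week 16 in composite IASI, analysed with a mixed-effect model: "The model will include treatment and treatment-by visit interaction as fixed effects and study subjects as random effects". The synopsis calls it a mixed-effect model repeated measures and adds no covariates. Neither place states a covariance structure beyond the subject effect.

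Section 9.3 adds that "final results will be presented as percent changes from baseline, calculated from the least square means of the model above". It does not say whether the response is the change score or raw IASI with baseline as one of the visits.

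Both omitted variables are available on everyone. Section 6.1.9: "Severity evaluations will be performed at every study visit". Section 5.4: "Randomization will be stratified by disease subtype (ARCI-CIE, ARCI-LI, EI and NS) in random blocks of 4". Section 9.3 uses subtype only for descriptive subgroup means.

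Section 9.5 sizes the trial on a two-tailed t-test of change: "Assuming a correlation between the pre and post treatment IASI scores of 0.55", with a cohort mean of 28.9 and SD of 9.0, a change SD of about 8.5, and 16 per arm for 80% power. It then says: "To account for an anticipated 20% dropout rate, 20 subjects in each treatment group (total 40) will be randomized". The primary analysis set in section 9.1 is "defined as all randomized patients who received at least one dose of the randomized treatment".

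**The concern.** A change score subtracts the whole baseline value, which is a slope of 1. With equal SDs and a pre-post correlation of 0.55, the best slope is 0.55. The difference remains as avoidable noise in the primary test of a 40-patient trial in rare diseases, where each extra patient is costly. Adjusting for baseline removes that noise with data already collected. A stratified randomisation is also normally reflected in the analysis, and here it is not.

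Two gaps in section 9.3 bear on the remedy. The correct use of baseline depends on whether the response is the change score or raw IASI with baseline as a visit. A model with only a subject random effect also relies on equal correlation between all visits, which the plan does not claim.

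**Working it through.** **Inputs.** From section 9.5: baseline mean 28.9, SD 9.0, r = 0.55 (the plan's assumption), two-sided 0.05, 16 per arm evaluable and 20 randomised. Effect: 30% of baseline, 0.30 × 28.9 = 8.67 points.

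**The plan's own figure.**
- SD of change = 9.0 × √(2 × (1 − 0.55)) = 8.54 (stated as about 8.5).
- Standard error = 8.538 × √(2/n) = 3.02 at n = 16 and 2.70 at n = 20.
- Noncentral-t power on 2n − 2 df: 79.4% at 16 per arm (79.7% with SD 8.5) and 87.9% at 20. The stated 80% reproduces.
- 16/0.8 = 20 per arm, as stated.

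**With baseline.**
- Residual SD = 9.0 × √(1 − 0.55²) = 7.52.
- Variance ratio = (7.516/8.538)² = 0.775.
- Allowing for chance baseline imbalance (variance factor 1 + 1/(2n − 4), 2n − 3 df), power is 87.2% at 16 per arm and 93.9% at 20.

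**With baseline and subtype** (four levels, assumed to explain nothing; factor 1 + 1/(2n − 7), 2n − 6 df).
- n = 16: SE = 7.516 × √(0.125 × 1.040) = 2.71, df 26, power 86.8%.
- n = 20: SE = 7.516 × √(0.100 × 1.030) = 2.41, df 34, power 93.7%.
- The three subtype terms cost 0.4 and 0.2 points here, and at most 0.5 in any run.

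A simulation of 40,000 trials per scenario agrees: 79.1% to 86.8% at 16 per arm, and 87.7% to 93.7% at 20. Mean 95% CI half-width falls from 6.12 to 5.52 points and from 5.43 to 4.87.

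**If the entry cut-off narrows baseline.** Section 4.1 says "Subjects must have an erythema score of at least 18 on IASI and an IASI-E score of 12". The wording is ambiguous; reading the first figure as composite IASI ≥ 18 is an assumption. Holding the slope (0.55) and residual SD (7.52) fixed, SD of change = √(7.516² + (0.45 × baseline SD)²). For a baseline SD of 6.98 that is √(56.49 + 9.87) = 8.15. Effect 8.67, baseline plus subtype, gains taken before rounding:

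| Reading | Baseline SD | Power, 16 per arm | Gain | Power, 20 per arm | Gain |
|---|---|---|---|---|---|
| No narrowing | 9.0 | 79.4% to 86.8% | +7.5 | 87.9% to 93.7% | +5.8 |
| Composite ≥ 18, no ceiling | 7.49 | 82.1% to 86.8% | +4.7 | 90.0% to 93.7% | +3.7 |
| Composite 18 to 48 | 6.98 | 83.0% to 86.8% | +3.9 | 90.6% to 93.7% | +3.1 |
| Composite ≥ 18 and IASI-E ≥ 12, subscores 0 to 24 | 5.90 | 84.5% to 86.8% | +2.3 | 91.8% to 93.7% | +1.9 |

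The last row uses the 0.73 correlation of composite IASI with IASI-E given in section 1.4. If the effect is instead 30% of the higher mean of selected patients, the three narrowed rows fall to +4.0/+2.8, +3.4/+2.4 and +1.9/+1.3.

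**Over the assumed correlation** (simulation, both sample sizes; narrowing taken as composite 18 to 48).
- r = 0.4: +11.4 to +12.8 without narrowing, +5.8 to +7.4 with it.
- r = 0.7: +1.4 to +2.2 without narrowing, +0.4 to +1.1 with it.

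**The repeated-measures model.** If correlation is constant across visits (0.55, 0.70 or 0.85 post-baseline), the random-intercept model on change scores gains +7.6 to +8.1 at 16 per arm and +5.7 to +6.1 at 20. These gains hold only under that constant correlation. If correlation decays over visits (AR(1), 0.55 between baseline and week 16, an assumption), null rejection at week 16 was about 11% to 15% for the unadjusted random-intercept models. It was about 10% for the random-intercept model with baseline added, and about 5% for week-16 ANCOVA.

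**The case against.** The plan is coherent as written. Section 9.5 sizes the trial on an unadjusted test of change, section 9.3 analyses change, and the power reproduces. With all 20 per arm observed, unadjusted power is already about 88%, so the gain is optional. The size rests on an assumed correlation and an ambiguous entry criterion. Subtype brings no demonstrated precision. If section 9.3 means raw IASI with baseline as a visit, baseline is already in the model as an outcome, and what is missing is only a common baseline mean. Adding baseline while keeping a random intercept would also leave the covariance weakness in place.

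Most of this stands as a limit on the point. It is why the point is an improvement rather than a correction, why the gain is given as a range, and why the fix specifies the covariance and treats the two readings of the response separately. It does not remove the point: on neither reading does section 9.3 use baseline efficiently. Under the raw-score reading with constant correlation, equalising the baseline means gave a similar gain, +7.4 at 16 per arm (81.2% to 88.5%) and +5.8 at 20 (88.9% to 94.7%).

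**Conclusion.** The omission is real and the remedy is a free improvement. At the plan's inputs, power rises by about 8 points at 16 per arm and 6 at 20. With complete data assumed at each size, the true figure lies between the two. In practical terms, 16 adjusted completers per arm (86.8%) come close to 20 unadjusted (87.9%). The gain is about 2 to 5 points if the entry cut-off narrows baseline, and can fall below 2 if the effect also scales with the selected mean. The documents give no SD for enrolled patients and do not say whether the cohort of 21 met the cut-offs. Over r from 0.7 to 0.4, with and without narrowing, the range is about 0.4 to 13 points. All of the quantified gain comes from baseline; subtype is included to match the randomisation.

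A reader might infer that the primary comparison is biased or the trial underpowered because these terms are missing. The documents do not support that: randomisation protects the comparison, and the stated power holds without adjustment. A reader might equally infer that the planned mixed model is valid in every respect. That is not established either, because section 9.3 gives no covariance structure beyond a subject effect. The finding of no bias concerns the omitted covariates only.

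**What to change.** Before the unblinded week-16 analysis, amend section 9.3 to state:

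- **Response:** change from baseline in composite IASI at weeks 4, 8, 12 and 16, with baseline not also an outcome visit.
- **Fixed effects:** treatment, visit, treatment × visit, baseline composite IASI, baseline × visit, and disease subtype (four levels).
- **Covariance:** unstructured within subject, with Kenward-Roger degrees of freedom, in place of a random intercept alone.
- **Fallback if the model does not converge:** ANCOVA at week 16 on the same covariates.
- **Percent changes:** name the denominator, for example the overall mean baseline IASI.

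If raw IASI with baseline as a visit is preferred, constrain the baseline mean to be equal across arms, keep subtype and the unstructured covariance, and do not add baseline as a covariate. Any mixed-model power gain quoted in support should be labelled as assuming constant correlation across visits.

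The cost is a wording amendment. Section 11.1 requires submission to the IRB and, if the change is judged to affect validity, approval by the IRB and Novartis Medical Affairs before use. No new data or visits are needed. At week 16, baseline uses one degree of freedom and subtype three, already charged in the table above.
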